2.6 Theory of change

The goal and the objectives of the project are based on the following theory of change (Figure 4).

Figure 4: DYNAMIC project theory of change

3 STUDY DESIGN

The primary intervention (i.e. ePOCT+ implementation) study will be conducted in two phases, with the study design detailed below and summarized in **Figure 5**.

3.1 Phase 1: cluster randomized controlled study in 40 health facilities

The ePOCT+ tool, as well as the complementary training and supervision tools, will be provided to HCWs of 20 of the 40 selected PHC facilities (intervention arm) in Morogoro and Mbeya regions, while the other 20 HFs will serve as controls (control arm), using a cluster randomized controlled study design. Randomization (1:1) of HFs will be done by region and HF type. Sick children aged 1 day to 14 years will be managed in accordance with the study arm to which the HF they attend has been assigned. The comparator for phase 1 will be routine care as currently implemented in Tanzania (see Section 8.1.5 for more detail). To assess the primary and secondary outcomes, final decision on referral, diagnoses and treatments at initial consultation will be recorded by HCWs electronically; children will also be followed-up by a phone call to their caregiver at day 7 to determine their final health status. Due to the pragmatic nature of the study, the design is adaptive in nature, where changes to the implementation may be incorporated throughout the study to account for issues

encountered in monitoring data and feedback from the field. These changes apply to the implementation context and exclude significant adaptations of the algorithm.

The purpose of Phase 1 is to compare the effect of using ePOCT+ with routine case management of sick children on the rational prescription of antibiotics, while ensuring a favorable clinical outcome. To date, a prior version of the ePOCT tool was assessed in conditions closer to that of an explanatory trial (Keitel et al., 2017). The present study is designed as a pragmatic randomized controlled study to assess the safety and impact on antibiotic prescriptions of implementing ePOCT+ (including its associated POC tests), supported by initial and continuous training and targeted supervision of health workers, in children attending Tanzanian primary health care facilities. The study will be implemented in settings of targeted future use and involving routine health care personnel, and include all sick children (except those coming for a follow-up visit in the context of a chronic condition). ePOCT+ provides support to HCWs in managing these sick children. Since the intervention takes place at the health provider level and that their practices are influenced by the context of the HF they are working in, randomization at HF level rather than at HCW level or at individual patient level was chosen.

[figure not shown]
3.2 Phase 2: scale-up of the intervention to 100 health facilities and transformation into a dynamic algorithm

The ePOCT+ tool will be extended to the 20 HFs serving as controls in Phase 1, as well as up to 60 additional neighboring facilities of our target area, to reach a total of up to 100 facilities (around 60 in Morogoro and 40 in Mbeya). In Phase 2, an adaptive study design will be used measuring the same outcome indicators as in Phase 1. The medical content of the algorithm will no longer be static, but rather modifiable according to the local data captured by ePOCT+ during Phase 1. Each modification will be designed and evaluated by the clinical expert group for its coherence, safety and potential benefit. Modifications in the algorithms designed to perform as well as the original algorithm but using fewer/different resources will be implemented in the facilities they were designed to serve (for example, if certain facilities do not have access to a certain resource). Similarly, modifications designed to personalize the algorithm according to demographic characteristics, geography or season will be implemented on the target population for which they were intended. Modifications of ePOCT+ aimed at improving health outcomes of subgroups of patients (for example those with respiratory infections) will be implemented in a sub-study where patients are randomized at an individual level. Modifications confirmed as safe and useful will then be implemented, while the non-beneficial changes will not be retained.

Examples of algorithm modifications expected to have positive impacts that will be explored for implementation are: 1) adapting the frequency of malaria testing in areas with very low endemicity; 2) improving the accuracy of pneumonia diagnosis, including , including through the use of novel POC diagnostic tools; 3) assessing the utility of using dengue rapid tests if an outbreak occurs; 4) or typhoid rapid tests in areas of high prevalence; 5) improving the prediction of severe disease; 6) improving the algorithm for malnourished or HIV positive children and; 7) testing sick children for sickle cell disease.

Figure 5: Study design overview.

3.3 Syndromic surveillance enhanced by microbiological testing

The syndromic surveillance (i.e. based on the clinical data generated by the use of ePOCT+) will be enhanced by microbiological surveillance in a few sentinel HFs, as well as in any facility according to abnormal data patterns detected by ML (based on predefined clinically supervised thresholds) to identify potential outbreaks or endemic diseases requiring specific attention.

Three to four HFs in each study district (6 to 8 in total) will be selected to play the role of sentinel sites, representative of different epidemiological conditions. In these HFs, blood, stool, urine or nasopharyngeal samples will be regularly collected from targeted sub-groups of children at risk of diseases of specific interest for surveillance (e.g. watery diarrhea to detect cholera or unspecific fever to detect dengue). In these sentinel sites, when attending a child presenting with one of the syndromes of interest (based on the data entered in the ePOCT+ tablet), the HCW will automatically see an additional screen requesting to collect the necessary additional sample (e.g. stool in case of diarrhea or blood in case of unspecific fever), if the patient has provided informed consent for that.

If a child presents a syndrome of specific interest for surveillance (e.g. fever and rash) due to pathogens that cannot be detected based on a day 0 sample only (e.g. *Rickettsiosia* or *Leptospira*), he/she would be asked to return to the facility at day 7 or later and provide an additional sample. In such rare cases, the child would most likely not be cured at day 7 and would need to return to the facility for further care anyway. If the result turns out to be positive for one of these pathogens, the child will be proposed specific treatment if necessary (see chapter 8.1.3).

In addition to sentinel sites, machine learning anomaly detection will be developed to visualize spatiotemporal clusters of events, which aims to help clinicians detect disease outbreaks (e.g. fever combined with abdominal tenderness in a cluster of households may be indicative of an outbreak of typhoid or another intestinal pathogen). The use of additional available spatiotemporal data sources will be explored in further developing the surveillance platform based on well-known risk factors of

diseases in the area that are prone to outbreaks. For example, remotely sensed data from satellite imagery may be incorporated to monitor environmental conditions (e.g. land surface temperature, rainfall, vegetation cover) known to influence seasonal patterns of some diseases. Likewise, information about the locations of water and sanitation features can be incorporated to help identify areas that are at increased risk of waterborne or water-related diseases.

3.4 Mixed-methods operational research

Throughout Phases 1 and 2, as well as during the last year of the project, mixed-methods studies will be conducted in HFs and communities, as well as at district and national levels, to understand the contextual factors that facilitate or impede the implementation, sustainability and scale-up of digital health interventions such as ePOCT+ in PHC settings. Examples of such factors may include socioeconomic and ecological profiles of communities, working conditions of the clinicians in the HFs, among others.

3.4.1 Cross-sectional quality of care surveys

Before the start of phase 1, during the second half of phase 1, and around 6 months after the beginning of phase 2, three cross-sectional surveys in a subset of randomly selected HFs will be performed to assess the quality of the consultation done by HCWs and their level of compliance to the algorithm (and thus to guidelines). Among the 40 HFs included in Phase 1, 18 HFs (10 in Morogoro and 8 in Mbeya, half of them being intervention HFs and the other half control HFs) will be randomly selected. Observers will be trained to attend and observe (without interfering) 25 consecutive consultations with children aged 1 day to 14 years per HF, thus a total 450 HCW/child pairs. Changes over time will be assessed during the three cross-sectional surveys. Before-and-after intervention analysis will be performed between the baseline analysis and the phase 1 intervention arm HFs, as well as between the control arm HFs in phase 1 and those same HFs that will then use the ePOCT+ tool in Phase 2. For the9 intervention HFs, this will provide another way (besides data recorded through the ePOCT+ tool) to measure potential improvement in the quality of the consultation over time. The tools for the quality of care surveys can be found in **Appendix 1**.

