	Syndromic surveillance enhanced by microbiological testing: Syndromic surveillance (i.e. based on the clinical data generated by the use of
	Three cross-sectional surveys in a subset of randomly selected HFs will be performed to assess the quality of the consultation done by HCWs and their level of compliance with the algorithm. Among the 40 HFs included in Phase 1, 18 (10 in Morogoro and 8 in Mbeya, half interventions and half controls) will be randomly selected. 25 consultations per HF will be observed for a total 450 HCW/child pairs. The survey will be performed once before the start of the study, once during Phase 1 and again approximately 6 months later during Phase 2 in the same facilities, with the aims of assessing changes in the use of ePOCT+ over time in the initial intervention facilities and a before-and-after ePOCT+ analysis in the initial control facilities.
	Cross-sectional quality of care surveys:
	Examples of algorithm modifications expected to have a positive impact that will be explored for implementation are: 1) adapting the frequency of malaria testing in areas with very low endemicity; 2) improving the accuracy of pneumonia diagnosis; 3) assessing the utility of using dengue rapid tests if an outbreak occurs; 4) or typhoid rapid tests in areas of high prevalence; 5) improving the prediction of severe disease; 6) improving the algorithm for children with chronic conditions (malnutrition, HIV or sickle-cell). Other type of changes might also be tested if considered important by the clinical experts.

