	which will require a much larger sample size due to the rareness of the event. In addition, the testing of differences in antibiotic prescription is conditional on satisfying non-inferiority in the clinical outcome. Assuming a cure rate of 97% in the control arm based on previous studies, the acceptable absolute non-inferiority margin will thus be one third of 3% (100%-97%), thus 1%. We assumed a cluster size of 900 patients and an intraclass correlation coefficient of 0.002 in the clinical outcome based on similar studies. To have 80% power to detect this difference of ≥1%, for a one-sided hypothesis test at alpha of 0.025, we would require 19 clusters and 17,100 patients per arm (total patients n=37,620 assuming 10% loss to follow-up), rounded to a total of 40 HFs and 40'000 patients. For Phase 2, sample sizes for the randomized sub-studies, aimed at evaluating the effect of a modification in the algorithm leading to a potential positive impact, will be calculated following the same general principles. In Phase 2, we expect that an average of 200 children per month per HF will be managed using ePOCT+, which corresponds to around 500,000 consultations over 2 years in the 100 HFs selected on predefined criteria.
Study duration	Phase 1 (including pilot phase): January 2021 – March 2022 Phase 2: April 2022 – October 2023 Implementation research: January 2021 – January 2023 Sustainability assessment: January 2023 – March 2024 Diseases Surveillance: October 2021 – March 2023
Study schedule	Cluster-randomized controlled study data collection (Phase 1): Sep 2021 – Mar 2022 Data collection for the evaluation of the spatiotemporal/prognostic adaptations of ePOCT+ (Phase 2): Apr 2022 – Oct 2023
	Data collection for the evaluation of the smart disease surveillance and outbreak detection system: Oct 2021 – Mar 2023
	Data collection for the cross-sectional mixed-methods studies: Jan – Mar 2021; Jan – Mar 2022; Jan – Mar 2023
	Final data analysis of phase 2 and of the contextual evidence that drives sustainability and future scale up: Jan 2023 – Mar 2024
Ethical statement	The research project will be carried out in accordance with the research plan outlined in this protocol and with principles enunciated in the current version of the Declaration of Helsinki, Essentials of Good Epidemiological Practice issued by Public Health Switzerland (EGEP) as well as all national legal and regulatory requirements as applicable.

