10.5 Analyses of data from operational research studies

Quantitative data from cross-sectional quality of care surveys, provider clinical competency or knowledge assessments, and caregiver and patient interviews will be analyzed using conventional statistical methods to compare means (t-tests or paired t-tests) or frequencies (chi-square tests) across intervention groups or time periods. Regression analysis may also be used to explore associations of multiple predictors with outcomes of interest.

All interviews and focus-group discussions will be audio-recorded with the participant's informed consent. Detailed notes will be taken during the interviews. Records will be manually transcribed in its original language (Kiswahili) and translated into English. A qualitative data analysis software (e.g. Nvivo) will be used to code the English interview transcripts in order to identify emerging themes. A predefined list of codes based on the interview guide and the recurrent themes highlighted in the detailed notes will be used. New codes will be created when new themes are identified during more detailed analysis of the transcripts. Deductive coding will be used to extract the themes based on the interview guide, but inductive coding will also be used to extract any unexpected themes that arise during the interviews.

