## 3.4 Statistical Interim analyses

No formal interim analysis was planned for the primary endpoints. However due to lower enrollment than expected after 8 months of recruitment, we planned an ad-hoc sample size recalculation to calculate the expected power of the study based on updated parameters. The power will be re-calculated using the actual clinical failure data from the control arm, adjusting the upper limit of the non-inferiority margin based on the risk ratio of 1.3, and taking into the actual enrollment numbers extrapolated up to mid-October 2022 (which corresponds to the end of 6 months of enrollment in all health facilities). All the other sample size calculation parameters will remain the same (see above)). The following approaches will therefore be undertaken based on the calculated power:

- If the updated sample size calculation finds a power of  $\geq 80\%$ , then the study will end as planned mid-October 2022.
- If the updated sample size calculation finds a power of  $< 80\%$  we will prolong the study, or increase the number of health facilities as required.

The sample size recalculation will be performed by an independent statistician, who will share the results of the updated sample size to the study investigators. To avoid implementation bias, the clinical failure proportion in the control arm will not be shared.

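### The baseline quality-of-care survey covers nine facilities in each arm, but the analysis named for it is a before-and-after contrast in the intervention facilities with no control term

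*Protocol*

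**What the plan says.** Protocol 3.4.1 selects "18 HFs (10 in Morogoro and 8 in Mbeya, half of them being intervention HFs and the other half control HFs", and observes "25 consecutive consultations with children aged 1 day to 14 years per HF, thus a total 450 HCW/child pairs". The survey is done three times: "Before the start of phase 1, during the second half of phase 1, and around 6 months after the beginning of phase 2". The synopsis says that the same facilities are used.

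Two before-and-after analyses are named. The first is "Before-and-after intervention analysis will be performed between the baseline analysis and the phase 1 intervention arm HFs". The second compares the Phase 1 control facilities with themselves once they use ePOCT+ in Phase 2; the synopsis calls it "a before-and-after ePOCT+ analysis in the initial control facilities". Neither has a stated comparator for change over time, and the second does not use the baseline survey.

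Protocol 10.5 gives t-tests, paired t-tests or chi-square tests "across intervention groups or time periods", and permits exploratory regression. The SAP does not cover the survey.

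Separately, the synopsis (procedures for Objective 1, secondary outcomes) names the survey as one of two data sources to be compared between arms.

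On dates, the synopsis schedule has "Data collection for the cross-sectional mixed-methods studies: Jan – Mar 2021; Jan – Mar 2022; Jan – Mar 2023". SAP 3.4 has enrolment running to "mid-October 2022 (which corresponds to the end of 6 months of enrollment in all health facilities".

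**The concern.** Observing 25 consultations in each control facility at baseline is useful mainly because it allows the controls' change to be set against the intervention facilities' change. The plan as written does not do this. It compares arms, or it compares periods, but never arms allowing for baseline.

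Common change between the two surveys is foreseeable. Protocol 8.1.6 gives control staff the paper guidelines and a reminder to follow them. SAP 3.1 describes the comparator as routine care plus clinical training equivalent to that in the intervention arm. Stock, staffing and supervision may also change over the year. All of this would be counted as an ePOCT+ effect in the before-and-after contrast.

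The outcome matters. The share of key symptoms and signs checked is a secondary outcome in Protocol 7.1. Control tablets record demographics and end-of-consultation decisions (8.1.7), and SAP 5.4 says that clinical signs are not systematically collected. The survey is therefore the only documented source for comparing arms on signs checked.

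**Working it through.** **The plan's own figure.** 18 facilities × 25 consultations = 450, as stated; 9 × 25 = 225 per arm per survey. No rate, power or intraclass correlation (ICC) is given for the survey, so every rate and correlation below is an assumption.

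**Bias.** Let s be the change common to both arms and e the ePOCT+ effect. The before-and-after contrast estimates s + e. The difference between the arms' changes estimates (s + e) − s = e. With e = 0, a baseline indicator of 50%, 225 v 225 consultations, a two-sided 5% test and clustering ignored:

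| Common shift s | Before-and-after estimate | Change relative to controls | Chance that the before-and-after test is significant |
|---|---|---|---|
| 5 points | 5 points | 0 | 18% |
| 10 points | 10 points | 0 | 57% |
| 15 points | 15 points | 0 | 90% |

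**Precision.** Take total variance 0.5 × 0.5 = 0.25, with between-facility part B = 0.25 × ICC and within-facility part W = 0.25 × (1 − ICC). Let c be the correlation of true facility levels over time. With 9 facilities of 25 per cell:
- concurrent arm comparison: variance 2(B + W/25)/9
- before-and-after in one arm: variance 2(B(1 − c) + W/25)/9
- change relative to controls: twice the before-and-after variance, so SE × √2 ≈ 1.4

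For ICC 0.05 to 0.20 and c 0.5 to 0.8, the SEs are about 0.07–0.11, 0.05–0.09 and 0.07–0.12 respectively.

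**Gain from baseline adjustment.** The reliability of a facility mean is 25·ICC/(1 + 24·ICC). This is 0.338 at ICC 0.02 and 0.735 at ICC 0.10. Multiplying by c of 0.5 to 0.8 gives a baseline-to-follow-up correlation r from 0.338 × 0.5 = 0.17 to 0.735 × 0.8 = 0.59. The adjusted variance relative to the unadjusted arm comparison is (1 − r²)(1 + 1/14), where the second factor allows for chance baseline imbalance with 18 facilities:
- r = 0.17: 0.97 × 1.07 ≈ 1.04, a slight loss
- r = 0.59: 0.65 × 1.07 ≈ 0.70, about 30% lower

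A pure change score has relative variance 2(1 − r), from 1.66 down to 0.82. It is worse than the unadjusted comparison whenever r < 0.5. Adjustment is therefore the better primary form.

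**Dates.** The SAP revision is dated 7 September 2022 and refers to 8 months of recruitment, so recruitment began about January 2022. Mid-October 2022 minus 6 months puts the last facilities at about mid-April 2022. The synopsis had Phase 1 data collection in September 2021 to March 2022, and a January–March 2022 survey falls in the later part of that period. In the period implied by the SAP, the same dates fall in its first months. For the third survey, 3.4.1 implies about October 2022 (Phase 2 from April 2022, plus 6 months), while the schedule says January–March 2023.

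**The case against.** The strongest reply is that quality of consultation already has a controlled, randomised comparison, because the synopsis compares the survey data between arms. This stands. A reader might infer that the plan has no controlled estimate of quality of care, and the documents do not support that. The before-and-after analyses are additional operational research.

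A reader might also infer that season is confounded. On the stated calendar it is not: the synopsis schedule and the timeline in Protocol 13.3 put all three surveys in the first quarter of successive years. A seasonal mismatch would arise only if a survey moved, and the documents do not say that one did.

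Nor do the documents show that some intervention facilities were surveyed before they had ePOCT+. The SAP dates concern enrolment in both arms; the late starters could be controls, or not among the 18.

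For Phase 2, the initial intervention facilities are not a clean control. They are already exposed, the algorithm becomes modifiable (3.2), and Protocol 12.2 says there is no control group. Subtracting their trend could add bias.

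Two points stand only in part. Section 10.5 permits regression that could include arm, period and baseline, but as an exploratory option and not a specified analysis. The documents also do not say whether control training came before or after the baseline observations. If before, that component causes no bias; other common change remains.

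**Conclusion.** The point holds for the named baseline-to-Phase 1 contrast: it has no control term, and 10.5 supplies none. Any common change passes into it in full. The 10-point shift and the 57% illustrate this and are not predictions, since the documents give no rates. The trial handles the same issue better elsewhere: SAP 6.3 uses the control arm to correct antibiotic trends for season, and Protocol 3.4.2 compares arms at baseline and end-line for staff competencies.

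The case rests on bias. A gain in precision over the unadjusted arm comparison is possible but not assured. The co-primary conclusions are unaffected, and the SAP's secondary list does not include the survey outcomes. This is a cheap improvement to the evidence on quality of care, together with a dating inconsistency to resolve.

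**What to change.** In Protocol 3.4.1 and 10.5:

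1. Make the Phase 1 effect estimate the between-arm comparison at the Phase 1 survey on facility means, adjusted for the same facility's baseline survey mean. Using facility means also deals with clustering, which the tests in 10.5 do not mention (design effect 1 + 24·ICC, or 2.2 to 5.8 at an assumed ICC of 0.05 to 0.20).
2. Report the intervention facilities' change from baseline to Phase 1 only beside the control facilities' change over the same two surveys. State that the before group is the 9 intervention facilities, since 3.4.1 leaves open whether it is those or all 18.
3. Label the Phase 1 to Phase 2 change in former control facilities as descriptive. Show it beside the change in the initial intervention facilities, noting that these are already exposed.
4. Reconcile the survey timing in 3.4.1 with the synopsis dates and the enrolment period implied by SAP 3.4, and survey both arms in the same calendar weeks. Timing counted from each facility's ePOCT+ start would not work, because controls have no such date in Phase 1.

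No extra survey, facility or observer is needed, and items 1 to 3 can be applied to surveys already done. The adjusted comparison costs one degree of freedom (residual 16 to 15). Its interval, or that of a change relative to controls (SE about 1.4 times), will be wider than that of the uncontrolled contrast.
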